Clinical Study Protocol

Use of Lexiscan™ for Myocardial Stress Perfusion Computed Tomography with a 3rd Generation Dual Source CT System

Principal Investigator: [name]

Origination Date: 07/06/2015

Medical University of South Carolina
Department of Radiology and Radiological Science
[name]
[name]

CONFIDENTIALITY STATEMENT

This document is the confidential property of Medical University of South Carolina, Radiology Department. No Part of it may be transmitted, reproduced, published or used by other persons without the permission of the Principal Investigator.

**Use of Lexiscan™ for Myocardial Stress Perfusion Computed
Tomography with a 3rd Generation Dual Source CT System**

Table of Contents

A. SPECIFIC AIMS	3
B. BACKGROUND AND SIGNIFICANCE	3
C. PRELIMINARY STUDIES	3
D. RESEARCH DESIGN AND METHODS (including data analysis)	4
D.1 Research Design	4
D.2 Statistical Methods / Sample Size Justification	10
E. PROTECTION OF HUMAN SUBJECTS	11
E.1 RISK TO THE SUBJECTS	11
E.1.a Human Subject Involvement and Characteristics	11
E.1.b Sources of Materials	14
E.1.c Potential Risks	14
E.2 ADEQUACY OF PROTECTION AGAINST RISKS	17
E.2.a Recruitment and Informed Consent	17
E.2.b Protection against Risk	18
E.3 POTENTIAL BENEFITS OF THE PROPOSED RESEARCH TO THE SUBJECTS AND OTHERS	19
E.4 IMPORTANCE OF THE KNOWLEDGE TO BE GAINED	19
E.5 SUBJECT SAFETY AND MINIMIZING RISKS (Data and Safety Monitoring Plan)	19
F. REFERENCES	22
G. FACILITIES AVAILABLE	22
H. APPENDIX	22

A. SPECIFIC AIMS

Primary Study Aim: The purpose of this study is to evaluate the feasibility, tolerability, safety, and image quality of low-radiation, dynamic perfusion CT of the heart in patients with suspected ischemic chest pain and a moderate or severe stenosis seen on coronary CTA.

The main hypothesis is that CTA with stress and rest perfusion imaging using Lexiscan™ as the coronary vasodilator will be safe, well tolerated, have lower radiation dose, acceptable image quality and be much faster than conventional nuclear perfusion imaging.

Secondary Study Aim: The secondary purpose of this study will be to assess the diagnostic accuracy of CT perfusion imaging compared to either SPECT, MRI stress perfusion, or invasive angiography.

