The SOMATOM™ Force is a new CT system, and currently no published data involving myocardial perfusion CT are available. However, the vendor has issued estimates on the enhanced performance of this new system that indicate a >20% reduction in radiation dose in all routine scans. Furthermore, cardiac imaging such as CTA and perfusion studies could result in up to a 50% reduction in total radiation dose. Given the technological advances detailed above we have confidence that these data will be realized in practice.

In addition, our research group has a proven track record of conducting CT studies on reductions in radiation dose and contrast material employing the previous generation of CT systems, such as the SOMATOM™ Definition and the SOMATOM™ Definition Flash. We have also conducted pioneering research in the novel applications of dual source CT with a focus on cardiovascular indications. In brief, these studies include the following:

- studies evaluating novel dose-lowering acquisition techniques such as ECG-dependent tube current modulation⁸, anatomic tube current modulation⁹, prospective ECG-triggering¹⁰ and high-pitch acquisition¹¹
- studies on optimizing contrast injection protocols¹²⁻¹⁵
- studies in specific patient populations such as obese patients¹¹ and pediatric patients^{9,12}
- studies using novel reconstruction techniques for dose reduction^{18,19}
- studies on specific difficult-to-image clinical scenarios, such as the evaluation of coronary stents²⁰⁻²¹ and heavily calcified coronary vessels²².

D. RESEARCH DESIGN AND METHODS (INCLUDING DATA ANALYSIS)

D.1 RESEARCH DESIGN

This study will include 100 adults who present to the MUSC ED, hospital, or outpatient clinic with a clinical history and symptoms suspicious for cardiac ischemia and who have undergone or will likely undergo nuclear stress testing (SPECT) or who have undergone MRI stress perfusion imaging.

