SPECT will be used as a comparator for the CT perfusion images. SPECT examinations will be interpreted for perfusion defects by two experienced readers (one nuclear medicine physician and one cardiologist). Images will be analyzed on a dedicated console using commercially available software. Evidence of ischemia will be determined by visual comparison of rest and stress SPECT perfusion scans as well as quantitative analysis available through the commercial analysis program. Perfusion defects will be visually rated as reversible, fixed, or mixed. Readers will be blinded to the results of CT perfusion data and invasive coronary angiography examinations.

Analysis of MRI stress perfusion images:

MRI stress perfusion imaging will be used as a comparator for the CT perfusion images. MRI examinations will be interpreted for perfusion defects by two experienced readers (one radiologist and one cardiologist). Images will be analyzed on a dedicated console using commercially available software. Evidence of ischemia will be determined by visual comparison of rest and stress MRI perfusion scans as well as quantitative analysis available through the commercial analysis program. Perfusion defects will be visually rated as reversible, fixed, or mixed. Readers will be blinded to the results of CT perfusion data and invasive coronary angiography examinations.

Image Quality:

Subjective assessment of image quality, coronary artery visualization, and perfusion images will be performed by two independent observers using a semiquantitative rating scale of 0 – 5. Image quality will be graded on a five-point scoring system: 1 non-diagnostic; 2 limited diagnostic value; 3 adequate (presence of artifacts not limiting detection of luminal stenosis); 4 good; 5 excellent.

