This study is intended to primarily demonstrate feasibility, safety, and tolerability of Lexiscan™ for use as a coronary vasodilator during perfusion CT imaging. The study is not powered to prove the diagnostic accuracy of perfusion CT imaging with low radiation compared to SPECT or the current gold standard approach of invasive coronary angiography with invasive fractional flow reserve (FFR) measurement. Nonetheless, we will use the available comparative data for each technique (SPECT, MRI stress perfusion imaging, and invasive angiography) to help design subsequent clinical trials that are adequately powered for an accuracy endpoint. We anticipate that about 15 out of the 30 participants who undergo the CT perfusion portion of the study will have available cath comparisons.

Continuous data are displayed as mean ± SD, if normally distributed, or median and interquartile range if not normally distributed. Binary data are are displayed as proportions. Data will be reported as means ± SD or rates with 95 percent confidence intervals. A difference with P value of 0.05 or less will be considered significant.

Subjective image quality scores will be compared using the Chi-squared test with the Yates continuity correction for categorical variables and inter-observer agreement for image quality will be calculated using Cohen kappa (K) statistics and interpreted as follows: ≤ 0.20 slight or poor agreement, 0.20 – 0.40 fair agreement, 0.40 – 0.80 moderate agreement, ≥ 0.80 excellent agreement. For each group, comparisons of patient characteristics will be performed using the Chi-squared test for categorical variables and t-test or Mann-Whitney-U-test for continuous variables as appropriate.

Quantitative data (CNR, radiation dose) will be tested using a non-parametric significance test.

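### The image quality score is ordered, but D.2 compares it by a Yates-corrected chi-squared test with no cut-point, comparator or pairing stated; this is not one defined test and does not estimate how often quality is acceptable

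*Combined protocol and SAP*

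**What the plan says.** Section A states the primary aim as to "evaluate the feasibility, tolerability, safety, and image quality of low-radiation, dynamic perfusion CT of the heart". The main hypothesis is that the examination will, among other things, "have lower radiation dose, acceptable image quality and be much faster than conventional nuclear perfusion imaging". It gives no score or proportion that would count as acceptable.

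D.1, Image Quality, defines the measure: "Subjective assessment of image quality, coronary artery visualization, and perfusion images will be performed by two independent observers". The range of the scale is first given in the words "using a semiquantitative rating scale of 0 – 5". The next sentence says "Image quality will be graded on a five-point scoring system" and labels levels 1 (non-diagnostic) to 5 (excellent). Zero has no label. The middle level reads "3 adequate (presence of artifacts not limiting detection of luminal stenosis".

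D.2 gives the only planned comparison of this score: "Subjective image quality scores will be compared using the Chi-squared test with the Yates continuity correction for categorical variables". Cohen's kappa follows, for agreement between observers. D.2 also says in general terms that rates will carry 95% confidence intervals and that p of 0.05 or less is significant. Its opening sentence restates the main intent as feasibility, safety and tolerability, without image quality.

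Older CT perfusion scans are named in D.1 as a comparator for the signal-to-noise and contrast-to-noise ratios, but not for the subjective score.

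**The concern.** The Yates correction is defined for a 2x2 table. A graded score becomes 2x2 only after it is cut, and there are four possible cuts on a 1–5 scale (five on 0–5). The alternative reading is an uncut 2x5 table, where the correction has no role and the test treats the grades as unordered labels. The plan chooses neither. It also does not say which sets of scans are compared or whether they come from the same patients; the named test assumes independent groups.

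The hypothesis is about an absolute level of quality. A non-significant difference from some other set of scans does not show that quality is acceptable, and a significant difference can arise between two good sets or two poor ones.

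If the scores are seen before these choices are made, the choices can change whether a difference is called significant.

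**Working it through.** The plan states no effect size, power or target for image quality, so it has no figure to reproduce. What follows is illustration on assumed data. Inputs from the documents: 0.05 threshold and 30 participants with CT perfusion (D.2); five labelled grades (D.1); total enrolment of 100 ("This study will include 100 adults who present to the MUSC ED, hospital, or outpatient clinic", D.1). Assumed: the comparator size, the score distributions, independent groups and two-sided tests.

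**1. One table, every reading.** Assumed counts at grades 1/2/3/4/5: group A 1/2/5/10/12, group B 2/5/10/9/4, each totalling 30.

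- *2x5 chi-squared.* With equal groups the expected count in each cell is half the column total. Each column adds 2 × (A − E)² / E: 2(0.25)/1.5 + 2(2.25)/3.5 + 2(6.25)/7.5 + 2(0.25)/9.5 + 2(16)/8 = 0.33 + 1.29 + 1.67 + 0.05 + 4.00 = 7.34 on 4 df, p = 0.12.
- *Yates 2x2.* χ² = N(|ad − bc| − N/2)² / (product of the four margins), with N = 60:

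| Cut | A below/at or above | B below/at or above | χ² | p |
|---|---|---|---|---|
| ≥2 | 1/29 | 2/28 | 60(30 − 30)²/(30·30·3·57) = 0 | 1.00 |
| ≥3 | 3/27 | 7/23 | 60(120 − 30)²/(30·30·10·50) = 1.08 | 0.30 |
| ≥4 | 8/22 | 17/13 | 60(270 − 30)²/(30·30·25·35) = 4.39 | 0.036 |
| ≥5 | 18/12 | 26/4 | 60(240 − 30)²/(30·30·44·16) = 4.18 | 0.041 |

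- *Mann-Whitney.* U = 621, so the estimated probability that an A scan scores higher, ties counted half, is 621/900 = 0.69; p = 0.009.

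Here the unstated cut alone moves the result across 0.05. That need not happen. On a second assumed table (1/3/8/12/6 versus 3/7/10/8/2) every reading of the planned sentence is non-significant (Yates 0.60, 0.13, 0.07 and 0.25; 2x5 0.23), while Mann-Whitney gives 0.019.

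**2. Power for a general shift.** Simulation of 20,000 trials per cell; proportional-odds shift with odds ratio 3; reference distributions (grades 1–5) of 3/10/27/40/20, 5/20/40/25/10 and 10/30/35/20/5%. Ranges are across the three.

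| Test | 30 v 30 | 100 v 100 |
|---|---|---|
| Mann-Whitney | 62–64% | 99% |
| 2x5 chi-squared | 38–39% | 94% |
| Yates, cut ≥4 | 36–46% | 91–96% |
| Yates, cut ≥3 | 6–36% | 43–91% |

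At odds ratio 1.5 and 30 versus 30, no test exceeds 14%.

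**3. A change confined to one threshold.** If scores of 1–2 only move up to 3 (20/20/20/25/15 to 3/5/52/25/15%, or 10/30/35/20/5 to 2/6/67/20/5%), at 30 versus 30 Mann-Whitney has about 27–41% power, the 2x5 test about 71–78%, and Yates at ≥3 about 78–79%.

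**4. The absolute question.** Exact (Clopper-Pearson) 95% intervals for assumed results: 27/30 = 90%, 73.5 to 97.9%; 90/100 = 90%, 82.4 to 95.1%.

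**The case against.** The strongest reply is that nothing depends on this test. No passage says that the chi-squared p-value decides acceptability. D.2 separately promises rates with confidence intervals, and grade 3, labelled adequate, is an obvious cut. No power was planned and no decision rule uses the result. D.2 also leaves image quality out of its restated intent. All of this is correct and limits the harm. It does not supply the missing definitions: no passage adopts grade 3 for analysis, and section A still lists image quality in the primary aim.

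A reader might infer that Mann-Whitney is always the better test. Step 3 shows that it is not. A reader might also infer from that scenario that the cut alone moves power from 3% to 79%, since Yates at ≥4 rejects in about 3% of trials. That would be wrong: the share scoring 4 or more is the same in both groups there (40% in the first case, 25% in the second), so the 3% is a false-positive rate.

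The stenosis wording at grade 3 could be read as meant for coronary images only. D.1 does not say so. It lists perfusion images among those rated and gives no other labelled scale.

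**Conclusion.** The concern holds and should be corrected, as a matter of analysis wording. The Yates-corrected test does not fit an uncut ordered score; scale, cut, comparator and pairing are all open; and a between-group p-value does not estimate how often quality is acceptable. These statements follow from the text and need no simulation.

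The size is illustrative. It rests on assumed distributions, independent groups and a comparator of equal size. At 30 versus 30 an ordinal test gains about 23 to 26 points of power over the 2x5 test for a shift of odds ratio 3. At 100 versus 100 most of that gap closes, though a Yates test cut at ≥3 can still fall to 43%.

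A reader might infer that the study is underpowered for image quality or will miss a stated target. The documents do not support that: they set neither power nor a target for this score. The consequence is that one part of the primary aim would be poorly answered.

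**What to change.** 1. Use one scale, 1 to 5, throughout D.1.
2. For perfusion scans and coronary CTA separately, report by reader the proportion scoring at least 3 with an exact 95% confidence interval, as the estimate of acceptable quality. State that no target proportion is set; the interval estimates acceptability and does not decide it.
3. For any comparison, name the comparator and say whether it is paired. Replace the Yates chi-squared test with Mann-Whitney if unpaired, reporting the probability of a higher score (ties counted half) with its 95% interval, or with Wilcoxon signed-rank if paired. Beside it, give the difference in the share scoring at least 3 with its 95% interval, because a change confined to that threshold shows better there.
4. For perfusion images, word the grade-3 anchor in terms of detecting a perfusion defect.

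Fix these before scores are seen. The planned signal-to-noise and contrast-to-noise measurements can stay as they are. The cost is a few sentences in D.1 and D.2, one anchor on the score sheet and slightly more analysis. Any comparator scans must be scored on the same scale.

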All measurements and calculations will be performed by one observer who will be blinded to image acquisition parameters. We will also measure the signal-to-noise ratio (SNR) and contrast-to-noise ratio (CNR) for the coronary CTA and the perfusion images. Circular regions of interest will be placed in the aortic root at the level of the left main coronary artery ostium (size 100 mm²) as well as in the proximal segments of the left and right coronary arteries and the left lateral ventricular wall (size 1 – 4mm²). Signal intensity (CT number in HU) and noise (HU standard deviation) will be recorded in each region. All regions-of-interest will be measured three times and mean measurements will be used for statistical analysis. The SNR will be calculated as the mean HU divided by the mean image noise measured in the aorta. The CNR will be calculated by subtracting the mean HU in the left lateral ventricular wall from the mean HU within the lumen of the proximal coronary arteries and dividing this difference by the image noise measured in the aorta.²⁶ These values (SNR and CNR), although standard measures of image quality in CT research, cannot be compared directly between CT and SPECT. However, they can be used as a quantitative gauge to compare image quality between the 3rd generation CT scanner with low radiation imaging and the older CT perfusion scans that required higher radiation exposure.

Analysis of radiation dose:

The CT dose index and dose-length product will be recorded by the scanner and collected for each image acquisition. Effective radiation dose will be calculated by using a standard conversion factor of 0.0145 for adult chest CT²⁷. For SPECT examinations, the effective radiation dose will be estimated by multiplying the administered activity of ^{99m}Tc-tetrofosmin with a tracer-specific conversion factor of 0.008 for rest and 0.0069 for stress acquisition. The effective radiation doses of rest and stress SPECT acquisition will then be combined to compute the net radiation dose²⁸. The radiation dose of the CT myocardial perfusion will be compared with the radiation dose obtained with the previous (older) scanner at our institution in order to have a direct comparison of the radiation exposure decrease to the patient. Patients who have MRI stress perfusion imaging as the comparative imaging study will be excluded from the radiation dose analysis.

Safety and Tolerability Assessment:

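### D.2 tests CNR only for a difference and plans no confidence interval for it, so a non-significant result cannot show that image quality held up at the lower dose

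*Combined protocol and SAP*

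**What the plan says.** Section A (Specific Aims) lists image quality among the four outcomes of the primary aim. It hypothesises that the CT examination will "have lower radiation dose, acceptable image quality and be much faster than conventional nuclear perfusion imaging".

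Section D.1, under Image Quality, adds an objective measure: "We will also measure the signal-to-noise ratio (SNR) and contrast-to-noise ratio (CNR) for the coronary CTA and the perfusion images". It notes that these ratios cannot be compared directly with SPECT, but that they can serve to "compare image quality between the 3rd generation CT scanner with low radiation imaging and the older CT perfusion scans that required higher radiation exposure".

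Section D.2 gives the analysis in one sentence, "Quantitative data (CNR, radiation dose) will be tested using a non-parametric significance test", with a study-wide rule: "A difference with P value of 0.05 or less will be considered significant". The test is not named, its sidedness is not stated, and SNR is not mentioned in that sentence. D.2 promises 95% intervals in general terms, for means or rates, but not for the difference between scanners. It gives no expected CNR loss, SD, number of older scans or power for this comparison. The remarks on limited power in sections A and D.2 concern diagnostic accuracy, not image quality.

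On numbers, D.1 states: "This study will include 100 adults who present to the MUSC ED, hospital, or outpatient clinic". D.2 anticipates that "about 15 out of the 30 participants who undergo the CT perfusion portion of the study will have available cath comparisons".

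**The concern.** Dose and CNR ask different questions. For dose the investigators hope to show a decrease, so a test that can reject no difference fits the purpose. For CNR the worry is that quality fell as dose fell, and the useful answer is how large a fall the data can exclude. A significance test does not give that answer. A P value above 0.05 can arise because CNR was preserved, or because the sample was too small or too variable to show a loss. The smaller and noisier the comparison, the more likely that result becomes.

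A report could then state that dose fell with no significant change in CNR, and readers would take this as evidence of preserved quality on a primary-aim outcome. The plan as written would provide nothing to show whether that reading was justified.

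**Working it through.** The plan states no figure for CNR, so there is none to reproduce. Its only related arithmetic, 30 patients × 17 segments = 510 regions in D.2, is correct and confirms 30 as the planning number for perfusion CT.

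**Inputs from the documents**
- Threshold 0.05 (D.2).
- 30 patients with perfusion CT (D.2) out of 100 enrolled (D.1).
- CNR measured on coronary CTA images as well as perfusion images (D.1, Image Quality).

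**Assumptions**
- Two-sided Mann-Whitney test, because the older scans come from other patients.
- Normal data with equal SD. Losses *d* are in SD units, from 0.2 to 0.8.
- 30, 60, 100 or very many older scans.

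**Power of the difference test**

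The efficiency of Mann-Whitney relative to the t-test is 3/π = 0.955, so

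SE = √[1/(0.955 n₁) + 1/(0.955 n₂)], and power = Φ(d/SE − 1.96).

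- 30 v 30: SE = √(2/28.65) = 0.264. At d = 0.5, power = Φ(1.892 − 1.96) = Φ(−0.068) = 47%.
- 30 v 100: SE = √(1/28.65 + 1/95.49) = 0.213. At d = 0.5, power = Φ(2.347 − 1.96) = Φ(0.387) = 65%.

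Power is 50% where d = 1.96 × SE and 80% where d = 2.80 × SE. With 30 new scans:

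| Older scans | Power at 0.2 SD | 0.4 SD | 0.5 SD | 0.8 SD | Loss with 50% power | Loss with 80% power |
|---|---|---|---|---|---|---|
| 30 | 11% | 33% | 47% | 86% | 0.52 SD | 0.74 SD |
| 60 | 14% | 42% | 59% | 94% | 0.45 SD | 0.64 SD |
| 100 | 15% | 47% | 65% | 96% | 0.42 SD | 0.60 SD |
| very many | 19% | 57% | 76% | 99% | 0.37 SD | 0.52 SD |

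Simulating the test at 30 v 30 (4,000 runs) gave 45% at 0.5 SD and 84% at 0.8 SD, slightly below the formula.

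With 100 new scans, power at 0.5 SD is 65%, 85% and 93% against 30, 60 and 100 older scans.

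**What an interval would show**

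The half-width of the 95% interval is about 1.96 × √(1/n₁ + 1/n₂) SD:
- 30 v 30: 1.96 × √(2/30) = 0.51 SD
- 30 v 100: 0.41 SD
- 100 v 100: 0.28 SD

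As an illustration, suppose the observed loss at 30 v 30 is 0.2 SD. The interval runs from −0.2 − 0.51 = −0.71 to −0.2 + 0.51 = +0.31 SD. The test says only that the difference is not significant. The interval says that a loss of 0.7 SD has not been excluded.

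**The case against.** The strongest case on the other side has four parts.

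- **Detection may be good.** A reader might infer that a real CNR loss would usually be missed. The documents do not support that. At 0.5 SD with 30 new scans, the loss is more likely missed than found only against 30 older scans; with 60 or more it is usually found. Section C expects a dose reduction of up to 50%. If noise rose as 1/√dose and nothing else changed, CNR would fall by 1 − √0.5 = 29%. Power at 30 v 30 would then be about 100%, 96%, 79% and 60% for assumed coefficients of variation of 20%, 30%, 40% and 50%. This part stands, and it limits the size of the point.
- **Thirty is not a firm number.** Coronary CTA images also yield CNR, and patients who enter after SPECT or MRI without a referral for CTA all receive the stress scan. This stands too. One hundred is an upper limit, since section F allows clinical CTA at another location.
- **A difference test can support the hypothesis directly.** A reader might infer that non-significance is the only result that could favour the new scanner. It is not: a significantly higher CNR would too, and section E.3 notes higher iodine attenuation at low photon energies. This stands, but it does not help if CNR is equal or modestly lower.
- **Acceptability has its own measure.** D.1 has two observers score image quality, with 3 as adequate, and D.2 plans kappa for their agreement. CNR against older CT is a supplementary gauge. This lowers the importance of the CNR result, but the reader scores do not say how much CNR was lost.

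The general promise of 95% intervals in D.2 is a partial answer at most, because an interval for each scanner's mean is not an interval for the difference.

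**Conclusion.** The point holds as a gap in the planned analysis, of minor to moderate weight. D.2 provides a test of CNR but no statement of how large a loss the data exclude, and a non-significant test cannot supply one at any sample size. With about 30 perfused patients, losses up to roughly 0.5 SD (30 older scans) or 0.4 SD (100 older scans) would more often than not be non-significant. Losses of 0.8 SD would usually be found. These figures rest on the assumed test, the assumed losses in SD units and assumed numbers of older scans. Power is higher if many more than 30 patients contribute CNR values.

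Two further inferences should be avoided. The plan nowhere says that P above 0.05 will be taken as acceptable quality; the risk lies in how the result may be read. Nor does the gap mean that the study needs a formal non-inferiority design. D.2 describes it as primarily a feasibility, safety and tolerability study, and the documents offer no basis for any particular margin.

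**What to change.** In D.2:

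1. Keep the non-parametric significance test for radiation dose.
2. For CNR and SNR, report the new-minus-older difference with its 95% confidence interval, for example the Hodges-Lehmann estimate, and give the number of older scans used.
3. State that P above 0.05 will not be read as comparable image quality.
4. Judge preservation by the size of loss that the lower confidence limit excludes, read alongside the observers' scores defined in D.1.
5. If the imaging investigators wish to claim that quality was preserved, they should state the largest acceptable loss before analysis. No particular margin is required here.

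The cost is a change of wording, with the same data and no extra patients. Step 5, if taken, also needs a judgement from the imaging investigators. The downside is a more guarded conclusion. For example, if 0.5 SD were chosen and there were no true loss, the chance that the lower limit clears it is Φ(0.5/√(1/n₁ + 1/n₂) − 1.96): 49% at 30 v 30, 67% at 30 v 100 and 94% at 100 v 100. At 30 v 30 an inconclusive result is therefore likely, and it would be an accurate account of what the data can show.
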